7.4 REPLACEMENTS

Educator and child participants may be replaced if they withdraw (or are withdrawn) between Stages of the research (either before Stage 1, or between Stage 1 and Stage 2). Participants will not be replaced if they withdraw within Stage 1 or Stage 2. Missing data will be removed pairwise in the event of within-stage dropout. In the event of considerable withdrawals and a compromised sample size, a second wave of data collection may be proposed (following HREC approval) to retain required sample size.

8. STATISTICAL METHODS

8.1 SAMPLE SIZE ESTIMATION, JUSTIFICATION, AND CALCULATION

The sample size will be 24 Child-Educator dyads. A target of 12 dyads will be in Group A and 12 will be in Group B. This sample size is selected as a pragmatic threshold due to the likely enrolment of 24-28 educators per training period with an approximate 50% recruitment rate. A sample size larger than 24 dyads is not feasible for the context of the current study. This calculation also allows for dropout of 10% which is consistent with previous similar investigations. This sample size is also comparable to other similar studies in early childhood education (cf McDonald et al., 2015).

Previous data with comparable outcome measures was used to estimate the intra-class correlation (ICC) in a similar setting of educators grouped by centre. For most outcome measures, the ICC was estimated to be 0.1 or lower. Assuming two educators per centre (cluster), with six centres per treatment, a standard deviation in change score of 0.3 (Piastra et al., 2012; Berry-Kravis et al., 2013), an ICC of 0.1, alpha 0.05 and power 0.8, the study should be powered to detect a difference of 0.358. This is comparable to the difference in change score of 0.4 that was previously observed (Piastra et al., 2012).

8.2 STATISTICAL METHODS TO BE UNDERTAKEN

All questionnaire data will be collected via Microsoft Teams and exported in raw format for processing in R or SPSS. Demographic information (including age, languages spoken, language proficiency, educator level of education, educator years of experience, and child communication measures [ASQ and PLS]) will be described for all dyad participants. Two multiple linear regression analyses will be conducted to address the primary aim (Stage 1 contrast) and our secondary aim (Stage 2 contrast). The outcome (dependent variable) for both analyses will be children's mean length of utterance Difference Score across each Stage. Independent variables will be Group allocation (A or B) and cluster (ECEC). This analysis plan will allow for the primary investigation to be conducted on data collected in Stage 1. This primary analysis will investigate the impact of group allocation (Training [Group A]; Control [Group B]) and cluster (Educator Centre) on children's language output (Mean Length of Utterance). The secondary investigation will be conducted on data collected in Stage 2. This secondary analysis will investigate the impact of group allocation (No-training follow-up [Group A]; Training [Group B]) and cluster (Educator centre) on children's language output.

Intention-to-treat analysis will be completed in the event of educator drop-out from the training. If appropriate, per-protocol analysis will be completed to investigate the primary and secondary outcomes.

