5. STUDY OBJECTIVES

5.1 RESEARCH QUESTIONS

This study will include two primary research questions relative to each participant group. Secondary research questions have also been identified for each participant group. Primary and secondary research questions are listed below.

5.1.1 Was the magnitude of change in children’s mean length of utterance greater during a period of educator training when compared to a control period with no training (Stage 1 comparison)?

5.1.1.1 Was the magnitude of change in children’s mean length of utterance during a training period comparable to a post-training follow up period (Stage 2 comparison)?

5.1.2 Was the magnitude of change in overall educator interaction skills observed greater during a period of educator training when compared to a control period with no training (Stage 1 comparison)?

5.1.2.1 Was the magnitude of change in overall educator interaction skills observed during a training period comparable to a post-training follow up period (Stage 2 comparison)?

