5.4 OUTCOME MEASURES

This research includes two primary outcome measures: (1) mean length of utterance¹ demonstrated by the child, and (2) a composite score of overall interaction strategies demonstrated by the target educator. These measures are consistent with previous research investigating children’s language development and adult-child interactions (Girolametto, Weitzman, & Greenberg, 2003; Girolametto, Sussman, & Weitzman, 2007; Piasta et al, 2012).

The outcome measures for the current study will be gathered from four 15-minute interactions between educator-child dyads collected before and after each training period. A difference score for each outcome measure will be calculated for each stage of training (differences between Time 2 and

¹ Mean length of utterance is a well-established measure of child language first described by Brown (1973). The calculation of mean length of utterance is based on the average number of morphemes produced per child utterance. It is an appropriate measure of language for young children (Ezeizabarrena & Fernandez, 2018).

Time 3 will produce Difference Score 1; change between Time 4 and Time 5 will produce Difference Score 2; time points are described in Figure 1 below).

Primary Outcome Measures:

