The primary outcome measure for educators will be the change in the composite score of overall interaction strategies demonstrated by the target educator in a 15-minute interaction with a child during a training period and during a period of no training. Eight target interaction strategies were defined by Speech Pathologists in WSLHD, with reference to the Teacher Interaction and Language Rating Scale (TILRS; Girolametto, Weitzman, & Greenberg, 2000) and the Conversational Responsiveness Assessment and Fidelity Tool (CRAFT; Friel, Wiggins, & Justice, 2007). Target interaction skills include three Child-oriented strategies, two Interaction-promoting strategies and three Language-modeling strategies. **Child-oriented strategies** include: (1) Encourages child to initiate by observing, waiting expectantly and listening, (2) Responds to the child's initiation with animation and specific language, and (3) Adjusts their position so that they are face to face with the child. **Interaction-promoting strategies** include: (4) Uses a variety of questions to stimulate conversations, and (5) Encourages turn taking. **Language-modeling strategies** include: (6) Uses a variety of vocabulary, (7) Expands the child's utterances by recasting and adding ideas, and (8) Extends the child's utterances by giving information about the topic. Each of these eight strategies will be coded as 'absent' (0) or 'present' (1) for each 30 second segment of the 15-minute interaction. An average will be taken for each strategy across all segments of the video. Then, all average scores will be summed to create a composite score of use of interaction strategies by educators. The presence of these skills will be coded by two members of the research team. These two members will score two video samples independently and meet to reach consensus on the presence of each strategy based on these two videos. The remaining video samples will be randomly allocated and coded by one of these two researchers; each of the two researchers will code 50% of the video samples each. Inter- and intra-rater reliability will be calculated based on 10% of the recorded samples.

The Primary outcome measure for children will be the change in mean length of utterance within a 15-minute interaction with an educator during an educator training period compared to a period of no training.

Secondary Outcome Measures:

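### Section 8.2 specifies no group comparison for the educator composite, one of the two declared primary outcomes

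*Protocol*

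**What the plan says.** Section 5 ranks the two outcomes equally.

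- Section 5.1: "This study will include two primary research questions relative to each participant group". The educator question is 5.1.2: "Was the magnitude of change in overall educator interaction skills observed greater during a period of educator training when compared to a control period" without training. It is labelled a Stage 1 comparison, and 5.1.2.1 is its Stage 2 counterpart.
- Section 5.2 puts a child part and an educator part into one primary objective, joined by an italicised *and*.
- Section 5.4: "This research includes two primary outcome measures". The second is "a composite score of overall interaction strategies demonstrated by the target educator". The same section later repeats it: "The primary outcome measure for educators will be the change in the composite score of overall interaction strategies demonstrated by the target educator".

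Section 8.2 states the analyses. There are two multiple linear regressions, one for Stage 1 (called the primary aim) and one for Stage 2 (called the secondary aim). "The outcome (dependent variable) for both analyses will be" the child MLU difference score for the stage, with group and centre (ECEC) as independent variables. Both analyses are then described again as concerning children's language output. The section ends with intention-to-treat and, if appropriate, per-protocol analyses, without giving a further model.

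Section 8.1 uses alpha 0.05 and power 0.8 once. It does not say which outcome the calculation is for.

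**The concern.** Silence about one outcome's model could be left to a statistical analysis plan. Section 8.2 is not silent: it counts the analyses, assigns each to a stage and names one dependent variable for both. The number two cannot mean one regression per primary outcome, because the regressions are defined by stage. An analysis plan that followed 8.2 would leave out question 5.1.2, and one that tested the composite would depart from 8.2.

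The Training is delivered to educators, so the composite is the outcome closest to the intervention. If the protocol is followed as written, the educator half of the primary objective gets no between-group test. If a test is added once results are known, its model and its role in declaring success will have been chosen after the fact.

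**Working it through.** **Sections side by side**

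| Question | Outcome | Stage | Rank in section 5 | Model in 8.2 |
|---|---|---|---|---|
| 5.1.1 | Child MLU | 1 | Primary | Yes |
| 5.1.1.1 | Child MLU | 2 | Secondary | Yes |
| 5.1.2 | Educator composite | 1 | Primary | None |
| 5.1.2.1 | Educator composite | 2 | Secondary | None |

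Elsewhere, 5.4 says only that a difference score is calculated for each outcome measure in each stage. That defines the variable; it is not a group comparison.

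**The protocol's own figure.** Inputs from 8.1: 12 dyads per group, two educators per centre, six centres per group, SD of change 0.3, ICC 0.1, alpha 0.05 (two-sided assumed), power 0.8.

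- Design effect = 1 + (2 − 1) × 0.1 = 1.10.
- Standard error = 0.3 × √(2 × 1.10 / 12) = 0.1285.
- Detectable difference, normal approximation = 0.1285 × (1.960 + 0.842) = 0.360, against 0.358 stated. Power at 0.358 is 79.6%. The figure reproduces closely, as one test at 0.05.

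**What a second primary does to it**

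- *Both must succeed, each at 0.05.* No alpha split is needed. With 80% power for each, joint power is 0.8 × 0.8 = 64% if the test statistics are independent, 69% at correlation 0.5 and 73% at 0.8. The correlations are assumptions.
- *Either may succeed, Holm at 0.05.* The first step tests at 0.025, so the detectable difference is 0.1285 × (2.241 + 0.842) = 0.396. Power at 0.358 falls from 79.6% to 70.7%, and power at 0.4 from 87.6% to 80.9%. This is a worst case for each outcome: once one hypothesis is rejected, the other is tested at 0.05.

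**Limit of these figures.** They apply to an outcome whose change score has an SD of 0.3. The composite is a sum of eight averages of 0/1 codes, so it runs from 0 to 8. Section 8.1 does not say whether 0.3 belongs to it or to MLU. Power for the composite cannot be calculated from the document.

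**Can the 8.2 model be copied to the composite?** Sections 5.6 and 5.8 allocate whole centres, so each centre lies in one group. With 12 centres as categorical terms, the design matrix has 1 (intercept) + 1 (group) + 11 (centre) = 13 columns but rank 12. The group effect cannot be estimated separately from the centre terms. The added model has to handle clustering in another way.

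**The case against.** The strongest reply is that the protocol does not abandon the composite. Its difference scores are to be calculated in each stage, 8.2 mentions per-protocol analysis of primary and secondary outcomes, and a statistical analysis plan that we have not seen may supply the model. This limits the claim: the document does not show that the composite will go untested, only that it specifies no group comparison for it. It does not remove the contradiction, because 8.2 states positively what both analyses are.

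Four stronger readings are tempting, and the protocol does not support them.

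- *A family-wise error of 9.75%.* Two independent tests at 0.05 give 1 − 0.95² = 9.75%, but only if either result alone counts as success. The protocol never says so, and the *and* in 5.2 points the other way. Even on the either-wins reading, the figure is 9.1% at correlation 0.5 and 7.0% at 0.9. A multiplicity rule is also something a protocol may leave to its analysis plan.
- *A conflict over the secondary aim.* Section 5.3 lists other child measures as secondary, so the Stage 2 label in 8.2 may look wrong. But 5.1 announces secondary questions and nests the Stage 2 comparisons under each primary, so the label agrees with 5.1.
- *Secondary measures left without analysis.* Section 5.4 says that their difference scores will be compared. Detailed models for them can be left to an analysis plan.
- *A detectable difference rising from about 0.40 to 0.45.* A t test on 10 degrees of freedom (12 centres) gives 0.399 at 0.05 and 0.455 at 0.025. The protocol's baseline is 0.358, which its normal approximation nearly matches; on that basis the change is 0.360 to 0.396. The choice of degrees of freedom is a separate matter.

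**Conclusion.** The point holds as an internal contradiction. Two primary outcomes are declared in 5.1, 5.2 and 5.4, and 8.2 fixes analyses for one of them. One of two primary questions (5.1.2) and one Stage 2 question (5.1.2.1) have no specified group comparison. This rests on the text alone and needs no numerical assumption.

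The numerical consequences depend on a decision rule the protocol has not stated: joint power of about 64% to 73% if both must succeed, or a detectable difference of 0.396 instead of 0.360 if either suffices under Holm. Both assume a two-sided alpha of 0.05. The first also assumes 80% power for each outcome and a correlation of 0 to 0.8; the second assumes that the SD of 0.3 applies to the outcome tested. Because the point settles what the primary analysis is, it should be resolved before outcome results by group are seen.

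**What to change.** Amend 8.2 in one of two ways.

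1. *Keep both primaries.* Add a Stage 1 model (primary) and a Stage 2 model (secondary) for the educator composite difference score. Account for clustering by centre without fixed centre terms that alias group, for example with a random centre effect and small-sample degrees of freedom, or by analysing centre means. State in one sentence how the two primaries determine success: both required, each at 0.05, or either sufficient, with Holm at an overall 0.05.
2. *Keep 8.2's choice of outcome.* Name child MLU the sole primary and reclassify the composite as secondary in 5.1, 5.2 and 5.4.

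In either case, 8.1 should say which outcome the SD of 0.3 and the previously observed difference of 0.4 describe.

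The cost is a few sentences and, under the first option, two extra model runs on data already collected. The stated power also becomes less favourable: lower joint power if both must succeed, or a slightly larger detectable difference under Holm. If small-sample degrees of freedom are used, the detectable difference should be restated on that basis (0.399 at 0.05 with 10 degrees of freedom); that shift comes from the method, not from the second primary. The second option avoids the cost of two primaries but gives up the composite's primary status.

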5.6 STUDY TYPE & DESIGN & SCHEDULE

This project will utilise an intervention-controlled, cross-over study design with two groups (see Figure 1). It will be a single-site study, completed within Integrated and Community Health in WSLHD and will be conducted across multiple ECECs within WSLHD .

Early childhood educators from ECECs within the Cumberland City Council Local Government Area will be enrolled to participate in the Training before the commencement of the current research. The Training is a continuing service that is currently provided by the speech pathology team in Child and Family Health within WSLHD. Two training stages will be conducted in 2021 and will form Stage 1 and Stage 2 of the current study.

All educators who are enrolled to attend the Training in 2021 will be invited to participate in the current study (see [Recruitment procedure](#) for further details). Following educator consent, each consenting educator will be paired with a child who meets the study inclusion criteria (see [Inclusion Criteria](#)) and educator-child dyads will be formed. These dyads will then be randomised in to one of two groups at the ECEC level: (1) Group A will receive training in Stage 1, (2) Group B will receive training in Stage 2 (see [Fig. 1](#)). Given this research design, only Group B will have a control period (8 weeks) and only Group A will have a follow-up period (8 weeks), in which no training is provided. Educators who do not provide consent to participate in the current study will still receive the training. No data will be gathered for the purposes of this research from participants who did not provide consent.

The study population will be adult early childhood educators who are enrolled in the Training and children (aged 24-42 months) with typically developing speech and language skills in their care at an ECEC within the Cumberland City Council Local Government Area. Young children (aged 24-42

months) were selected as the population of interest for the current study due to the influence of Trained adult interaction strategies on language learning in children this age.

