5.8 RANDOMISATION

Centres participating in the Training will indicate availability for either or both of the training periods. We will use the random number generator at <https://www.random.org/integers/> to allocate centres who indicate availability for both stages. Therefore, pseudo-cluster randomisation will be implemented, as centres who are available in one time period only will not be randomised for pragmatic reasons. Randomisation will occur at the cluster or centre level to avoid cross-contamination effects between trained and untrained educators. This will occur after educators and children have been recruited in to the current study. This pseudo-randomization is required for the current, pragmatic study.

Masking of educators to training (+training) and no training (-training) conditions is not possible as they are actively participating in the training. The speech pathologist who analyses interaction skills will be blinded to which time point the video is recorded in and the condition that the educator is assigned to (+ training or –training). Therefore, this is a single blinded study.

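### As worded, the Section 8.2 regressions contain both Group and centre, but centres are nested in Group, so the Group coefficient is not estimable

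*Protocol*

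**What the plan says.** Section 8.2 of the protocol gives the method: "Two multiple linear regression analyses will be conducted to address the primary aim (Stage 1 contrast"), with the second regression serving the Stage 2 contrast. The response is fixed too: "The outcome (dependent variable) for both analyses will be children's mean length of utterance Difference Score across each Stage". The predictors are stated in one sentence: "Independent variables will be Group allocation (A or B) and cluster (ECEC"). The section then says, once for each Stage, that the analysis will examine the impact of group allocation and of cluster on the child's language output.

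Allocation is by centre. Section 5.6 says: "These dyads will then be randomised in to one of two groups at the ECEC level". Section 5.8 says: "Randomisation will occur at the cluster or centre level to avoid cross-contamination effects between trained and untrained educators". Not every centre is randomised ("centres who are available in one time period only will not be randomised for pragmatic reasons"), but those centres also enter a Group as whole centres.

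Section 8.1 sets the size: "A target of 12 dyads will be in Group A and 12 will be in Group B". Its calculation begins: "Assuming two educators per centre (cluster), with six centres per treatment". It uses an SD of the change score of 0.3, an ICC of 0.1, alpha 0.05 and power 0.8, arrives at a detectable difference of 0.358, and cites a previously observed difference of 0.4.

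The protocol nowhere mentions a random effect, a mixed model, generalised estimating equations, a cluster-robust variance or an analysis of centre means.

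**The concern.** When every centre lies wholly in one Group, knowing the centre tells you the Group. A regression that already contains the centres as categorical predictors has nothing left from which to estimate Group. The comparison of interest lies between centres, and the centre terms absorb all between-centre variation.

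This is the only analysis the protocol states for research question 5.1.1 (child MLU, training against control), and the Stage 2 analysis repeats it. If it cannot deliver the training contrast, someone must choose another primary model, probably once the difference scores are available. The model also sits badly with Section 8.1, which treats centre as a source of correlation between dyads, not as a set of fixed predictors.

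**Working it through.** **Inputs.** From Section 8.1: 6 centres per Group, 2 dyads per centre, 24 dyads, SD 0.3, ICC 0.1, alpha 0.05 (taken as two-sided, since the sidedness is not stated), power 0.80, stated detectable difference 0.358, reference effect 0.4. From Sections 5.6 and 5.8: every centre belongs to one Group.

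**1. The plan's own figure.** Design effect = 1 + (2 − 1) × 0.1 = 1.1. SE of the Group difference = 0.3 × √(2 × 1.1/12) = 0.1285. With normal quantiles, the detectable difference = (1.960 + 0.842) × 0.1285 = 0.360, against 0.358 stated. The figure reproduces to within rounding, as a between-centre comparison with inflation for clustering.

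**2. Estimability of the 8.2 model.** The columns are the intercept, Group and 11 centre indicators, 13 in all over 24 rows. The rank is 12. Without Group the rank is still 12, so Group adds nothing and its coefficient is not estimable. The algebra does not depend on the number of centres or dyads and applies equally to Stage 2.

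**3. What software could return.** There are three outcomes.

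- *Centre entered first.* Group is the redundant term and has no estimate.
- *Group entered first, one aliased centre column dropped, coefficient read.* The Group coefficient is the mean of one A centre minus the mean of one B centre, using 4 of the 24 dyads. In one simulated data set (true effect 0.4, observed difference in means 0.42), three choices of reference centres gave 1.01, −0.04 and 0.53, with the same residual sum of squares (0.772 on 12 df).
- *Group entered first, sequential (ANOVA) test read.* This uses all 24 dyads but tests the between-centre contrast against within-centre error on 12 df.

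**4. Size of the second and third outcomes at ICC 0.1, in SD units.** The true variance of each contrast is proportional to 1.1, but the model's error term estimates 0.9. The variance is understated by a factor of 1.1/0.9 = 1.222. The 12-df critical value of 2.179 therefore acts as 2.179/√1.222 = 1.971, and P(|t| > 1.971) on 12 df = 0.072. Type I error is about 7.2% in both cases.

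The reference effect is 0.4/0.3 = 1.33 SD.

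| Contrast | True SE (SD) | Noncentrality | Power |
|---|---|---|---|
| One A centre vs one B centre | √1.1 = 1.05 | 1.33/1.05 = 1.27 | about 27% |
| Sequential test, all 24 dyads | √(2 × 1.1/12) = 0.428 | 1.33/0.428 = 3.11 | about 86% |

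**5. Omitting centre altogether.** An ordinary two-sample comparison of 24 dyads on 22 df has a simulated type I error of about 6.2% at ICC 0.1.

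**6. A valid analysis.** With Group fixed and centre random, or with centre means, there are 12 − 2 = 10 between-centre df. On the same SE of 0.1285, noncentral t gives power of 71% at 0.358 and 80% at 0.4 (80.0% in simulation for the t-test on centre means). The difference detectable with 80% power is 0.399.

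**The case against.** The best defence is that 8.2 names the variables without fixing their coding or the estimator. It does not say fixed or dummy-coded. Section 8.1 uses an ICC, so the authors knew that dyads within a centre are correlated, and listing cluster may be loose wording for allowing for that. A statistical analysis plan, not shown here, could specify a random effect. This stands in part, and it is why the point is limited to the text as worded. But a predictor in a multiple linear regression, whose impact is to be examined alongside that of Group, most naturally means a fixed term. A later plan that used a random effect would be changing the protocol's model, not filling in a detail.

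Entering centre as a numeric code makes the fit solvable, but it adjusts for an arbitrary label.

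A reader might infer that software would silently print a wrong training effect with 27% power. The documents do not support that. Section 8.2 names R or SPSS, and both normally report a redundant or undefined term. The 27% also belongs to only one of three possible outputs; the sequential test has about 86% power, at the price of type I error near 7%.

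A reader might also infer that leaving centre out would be seriously anti-conservative. At the protocol's ICC, which it puts at 0.1 or lower for most outcomes, the inflation is from 5% to about 6%. Larger figures need an ICC that the protocol does not give.

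**Conclusion.** The point holds for the text as worded: with centre as a categorical predictor, neither the Stage 1 nor the Stage 2 regression can estimate the Group contrast. That part is exact and needs only whole-centre allocation. It would be going too far to say that the trial cannot estimate the training effect. The design supports that contrast on 10 between-centre df; the fault is in the model sentence.

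The practical harm is most likely an unplanned choice of primary model after the data are seen. The choices differ materially: no estimate, an arbitrary two-centre contrast with about 27% power, a sequential test with about 7% type I error, or omission of centre with about 6%. These figures assume 12 centres of 2 dyads, ICC 0.1, a two-sided 5% level and, for power, an effect of 0.4 with SD 0.3. This should be corrected before analysis, because it concerns the only stated analysis of the child primary question.

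**What to change.** Replace the sentence on independent variables in Section 8.2 with: a linear mixed model for the MLU difference score, with Group as fixed effect and a random intercept for ECEC, using a small-sample degrees-of-freedom correction (Kenward-Roger or Satterthwaite), applied in the same form to Stage 1 and Stage 2. Reword the two later statements about the impact of cluster to say that centre is accounted for as a source of correlation.

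A two-sample t-test on centre-mean difference scores (10 df with 12 centres) is a simple alternative. It is equivalent only when cluster sizes are equal, which cannot be counted on: two educators per centre is a planning assumption, and Section 7.4 provides for dropout and replacement.

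The cost is wording in 8.2 plus a restatement of 8.1. On 10 between-centre df the detectable difference at 80% power is about 0.40 rather than 0.358, and power at 0.358 is about 71%. Power at the cited 0.4 remains about 80%, so the sample size argument survives, but with no margin. No new data are needed, and the mixed model can be fitted in the software already named.
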